^r Blood samples for PK analysis will be collected at the timepoints listed in Table 7 in all fitusiran arm patients. In East Asian patients in the fitusiran arm at East Asian sites, blood samples for PK analysis will be collected at the time points listed in Table 8 (which includes those time points listed in Table 7), and pooled urine for PK analysis will be collected at the time points listed in Table 9.

^s Must be completed at the clinic. Will be collected at EOS visit, not be collected at ET visit.

^t Will include review of entries, (symptoms of bleed events, bleed causality, bleed severity, doses administered), whether appropriate site contact occurred regarding treatment of bleeds, and review of patient bleed management plan and recommendations and requirements for site contact regarding dosing.

^u It is preferred that factor concentrate administration and bleeding events are entered in the eDiary immediately or within 24 hours. Additional patient follow-up may be required as described in Section 7.2.1. Patients in the fitusiran treatment arm who present in the clinic with symptoms characteristic of a potential bleeding episode should have assessments completed per Table 2.

^v Perioperative assessment of safety and hemostatic efficacy only in patients undergoing operative procedures while on study (see Table 10).

^w AEs will be monitored and recorded from date of signed informed consent through Follow-Up. Signs and symptoms of thrombosis will be evaluated at every visit (see Section 6.5).

^x In addition to recording concomitant medications, documented history of prior medications will be collected during Screening.

Table 2: Bleeding Episode Assessments – Unscheduled Visit

| | Predose | Postdose 10 min (± 5 min) ^d | Postdose 60 min (± 5 min) ^d |
|--|---------|--|--|
| Directed Physical Examination ^a | X | | |
| Vital Signs | X | | |
| AT | X | | |
| FVIII/IX Levels | X | X | X |
| TG | X | X | X |
| Coagulation | X | X | X |
| Hematology | X | X | X |
| Exploratory Coagulation ^b | X | | X |
| Optional Imaging ^c | X | | |

Abbreviations: AT=antithrombin; BPAs=bypassing agents; FVIII=factor VIII; FIX=factor IX; TG=thrombin generation

^a See Section 7.5.3 for assessments to be performed during a directed physical examination.

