3	This version	To update Per-protocol Analysis Set definition	The detail deviations are included in the Per-protocol analysis set definition in Section 4.
3	This version	To define Covid-19 Unaffected Set	Covid-19 Unaffected Set is defined in Section 4.
3	This version	To clarify baseline definition for fitusiran group	For fitusiran group only, baseline definition is changed from Day 1 to first dose date in Section 5.5
3	This version	To clarify the multiplicity adjustment for Haem-A-QOL endpoints	For the two Haem-A-QOL scores (physical health score and total score), physical score will be tested first followed by total score.
3	This version	To add patient disposition category for Covid-19 impact summary	Patients discontinue the treatment due to Covid-19 and patient discontinue the study due to Covid-19 are added in Section 6.1
3	This version	Due to the exclusion criteria 6, the analysis of fibroscan/fibrotest result at baseline against worst post-baseline ALT elevation is not necessary	The related analysis is removed in Section 6.6.3
3	This version	To add the efficacy analyses for ABR endpoints due to Covid-19 impact	For ABR, the sensitivity analyses on Covid-19 unaffected set is added in Section 6.3. In addition, a sensitivity analysis to exclude the bleeds during the period of missing at least 2 consecutive doses due to Covid-19 event is added in Section 6.3.

SAP version number	Date approved	Rationale	Description of statistical changes
3	This version	To update the analyses for Haem-A-QoL due to Covid-19 impact	For sensitivity analyses, ANCOVA model will be ran on Covid-19 unaffected set, on the set excluding data collected with Covid-19 impact, on the set of patients whose responses level to EQ-5D dimensions “anxiety/depression” is no change or improved from baseline.
3	This version	To add the sensitivity analysis for Haem-A-QoL baseline assessments	For sensitivity analyses, the same analysis as main but excluding values of those who completed Haem-A-QOL at baseline on the same day but after first dose of fitusiran.
3	This version	To add the AE summary related to COVID-19 infection	AE potentially consistent with COVID-19 will be summarized by SOC and PT and list will also be provided. The search term list is added in the Appendix 8.2
3	This version	To add AE summary by hemophilia type	By hemophilia type summary is added to key AE tables.

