3.2 Endpoints

3.2.1 Efficacy endpoints

Primary and secondary endpoints for Global and US protocols are in the table below

	Global Protocol	US Protocol
Primary	Annualized Bleeding Rate (ABR) in the efficacy period	ABR in the treatment period
Secondary	ABR in the treatment period	ABR in the efficacy period
	Annualized spontaneous bleeding rate in the efficacy period	
	Annualized joint bleeding rate in the efficacy period	
	Change in Haem-A-QOL physical health score and total score in the treatment period	
	ABR in the onset period	

Exploratory Efficacy Endpoints

- Change in the following in the treatment period:
 - Treatment Satisfaction Questionnaire for Medication (TSQM) domain scores
 - Haemophilia Activities List (HAL) score
 - Paediatric HAL (pedHAL) score
 - EQ-5D-5L index value and visual analogue scale (VAS) score
 - Haemo-QOL score
 - Hemophilia Joint Health Score (HJHS)
- Number of target joint bleeding episodes
- Annualized weight-adjusted use of factor concentrates
- Change in patient resource use (eg, work/school attendance, visits to doctor/hospital)

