 - Site provided incorrect stratification data in IRT for patient's randomization.
 - The subject initiated use of factor concentrates or bypassing agents as prophylaxis for bleeding episode prevention, including doses related to anticipated hemostatic challenges such as physical activity, during the treatment period but the study drug was not discontinued.
- PK Analysis Set: All patients who receive at least 1 dose of study drug and have evaluable PK data contributing to the estimation of PK parameters.
 - Operative Procedure Analysis Set: All patients who received at least 1 dose of study drug or were randomized to on-demand arm and underwent at least 1 operative procedure during the study.
 - Covid-19 Unaffected Set: All patients who had no major or critical protocol deviations due to Covid-19 at any visits up to end of study (Month 9).

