6.3.2.4 Haem-A-QoL

The Haem-A-QoL will be provided to patients ≥ 17 years of age and includes 46 items contributing to 10 QoL domains (physical health, feelings, view of yourself, sports and leisure,

work and school, dealing with hemophilia, treatment, future, family planning, partnership and sexuality). Scoring for each item is based on a 5-point Likert scale (never, rarely, sometimes, often, and all the time), and higher scores represent greater impairment. The change from baseline in physical health score and total score of Haem-A-QoL at the end of the study will be analyzed using an analysis of covariance (ANCOVA) model with fixed effects of treatment arm, randomization strata of number of bleeding episodes in the 6 months prior to study entry (≤ 10 vs > 10) and randomization strata of hemophilia type (A vs B), baseline Haem-A-QoL physical health score and total score as covariates. Least square means of the physical health score and total score in each treatment arm and the difference of the least square means of the physical health score and total score in the two arms (along with the 95% CI and p-value) will be presented. The normality assumption based on ANCOVA model will be examined and a sensitivity analysis based on the non-parametric Wilcoxon-Mann-Whitney test will be performed. Domain scores, standardized scale scores, and transformed scale scores for Haem-A-QoL and their changes from baseline will be summarized. The above ANCOVA analysis is based on observed data. For patient with missing assessment due to early withdrawal, a sensitivity analysis will also be performed by imputing the domain score and total score as the worst score if the reason of withdrawal is treatment-related in the corresponding treatment arm, and as the average score for other reasons of withdrawal that are not treatment related in the corresponding treatment arm. The same analysis as main will be performed as a sensitivity analysis by excluding values of those who completed Haem-A-QoL at baseline after first dose of fitusiran.

To evaluate the impact of Covid-19, the same ANCOVA model will also be repeated on Covid-19 unaffected set. In addition, a sensitivity analysis using same ANCOVA model will be performed excluding the data impacted by Covid-19 major/critical protocol deviation. A supportive analysis will be repeated on the patients whose responses level to EQ-5D dimensions “anxiety/depression” is no change or improved from baseline.

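### One supportive Covid-19 analysis of Haem-A-QoL selects patients on a post-randomization mood response and uses no pandemic criterion

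*SAP*

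**What the plan says.** SAP 6.3.2.4 gives three analyses under the Covid-19 purpose:

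1. "To evaluate the impact of Covid-19, the same ANCOVA model will also be repeated on Covid-19 unaffected set". SAP section 4 defines that set by the absence of major or critical Covid-19 protocol deviations.
2. The same model "excluding the data impacted by Covid-19 major/critical protocol deviation".
3. "A supportive analysis will be repeated on the patients whose responses level to EQ-5D dimensions", limited to the anxiety/depression item and to patients for whom it stayed level or improved since baseline.

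The change log in SAP 2.6 places the third analysis in version 3 with the rationale "To update the analyses for Haem-A-QoL due to Covid-19 impact", and describes it as run "on the set of patients whose responses level to EQ-5D dimensions" with the same condition. Neither section explains why this subset reflects the pandemic or how its result is to be read.

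EQ-5D is also an outcome of the trial. SAP 3.2.1 lists change in "EQ-5D-5L index value and visual analogue scale (VAS) score" among the exploratory efficacy endpoints, and SAP 6.3.3.3 plans counts by level for each dimension. Protocol Table 1 schedules EQ-5D and Haem-A-QoL at baseline and at the last visit, under a shared footnote: "Will be collected at EOS visit, not be collected at ET visit".

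**The concern.** A check for the pandemic should divide the data by something that marks the pandemic and that treatment cannot move. This subset does neither.

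- **It conditions on a possible effect of treatment.** A patient who became anxious because he kept bleeding is removed. If fitusiran relieves anxiety by preventing bleeds, more patients who are doing badly leave the on-demand arm than the fitusiran arm.
- **It overlaps with the outcome.** The Haem-A-QoL total score includes a feelings domain, so for that score patients are partly selected on what is being compared.
- **It does not identify pandemic exposure.** Worse mood from any cause leads to exclusion, and pandemic exposure without worse mood does not.

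The two Haem-A-QoL scores are the last step of the hierarchy in SAP 5.7, so Covid-19 results for them will be read as evidence of robustness. A smaller difference in this subset could be taken to mean that the benefit was due to the pandemic. Agreement with the main result could be taken as confirmation. The analysis supports neither reading.

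**Working it through.** **The plan's own figures.** The documents give no design figure for Haem-A-QoL or EQ-5D. The only one is for ABR, and it reproduces: (32 + 64)/(1 - 0.20) = 120. For power at one year of follow-up, k = (SD² - mean)/mean² gives 0.549 on demand and 2.0 on fitusiran. With the larger k in both arms, the variance of the log rate ratio is (1/18 + 2)/32 + (1/4 + 2)/64 = 0.0994. Then |ln(4/18)|/0.315 = 4.77 and power is 99.75%, consistent with the stated figure of above 90%. The point here does not depend on it.

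**Timing.** SAP 2.5 dates the first enrolment to 1 March 2018. Protocol Table 1 puts EOS at Day 253, which is Day 1 + 252 days. If Day 1 was 1 March 2018, EOS fell on 8 November 2018; after a full 60-day screening it fell in early January 2019. SAP version 2, dated 6 August 2019, lists no Covid-19 change. The earliest EOS assessments could therefore precede any Covid-19 provision in the plan, yet a patient whose anxiety had worsened by then is excluded.

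**Size of the bias (all inputs assumed).** Treat the anxiety change as a latent normal variable with SD 1, correlated rho with the Haem-A-QoL change. Keep a patient if the anxiety change is at most c, where c fixes the share of on-demand patients who worsen. Let fitusiran lower anxiety by s, and let L(x) = phi(x)/Phi(x), the normal density over the cumulative probability. The expected difference in the subset is

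true difference + rho × SD × [L(c) - L(c + s)].

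Take a true difference of -9, SD 15 and s = 0.4.

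- 25% worsen: c = 0.674, L(c) = 0.424, L(c + 0.4) = 0.261. With rho = 0.3 the bias is 0.3 × 15 × 0.163 = 0.73 points (8.1%). With rho = 0.7 it is 1.71 points (19.0%). Retention is 75% on demand and 86% on fitusiran.
- 40% worsen: c = 0.253, L(c) = 0.644, L(c + 0.4) = 0.434. With rho = 0.3 the bias is 0.95 points (10.5%). With rho = 0.7 it is 2.21 points (24.5%). Retention is 60% and 74%.

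**The direction is not fixed.** The next results are in SD units, with a true difference of -0.50. The arm-specific and no-true-difference results use 20% of on-demand patients worsening, so c = 0.842 and L(c) = 0.350.

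- s = 0 with equal correlations: no change.
- Fitusiran worsens anxiety by 0.2 SD: the difference becomes 104% to 115% of the truth, for rho 0.2 to 0.7 and 20% or 30% worsening.
- s = 0 with rho 0.5 on demand and 0.2 on fitusiran: -0.50 + 0.3 × 0.350 = -0.395 (79%). With the correlations swapped: -0.605 (121%). With s = 0.3 the two become about 75% and 110%.
- No true difference, s = 0.3, rho 0.5: 0.5 × (0.350 - 0.238) = 0.056 SD, a spurious difference against fitusiran.

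**Does the rule isolate the pandemic?** Assume 40% of patients are exposed, exposure worsens anxiety by 0.5 SD, and 20% of unexposed on-demand patients worsen. Exposed on-demand patients are kept with probability Phi(0.842 - 0.5) = 0.634, so overall retention is 0.6 × 0.80 + 0.4 × 0.634 = 0.733. Of those excluded, 0.6 × 0.20/0.267 = 45% were never exposed. Of those kept, 0.4 × 0.634/0.733 = 35% were exposed. In the fitusiran arm with s = 0.3 the shares are 42% and 36%.

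**The case against.** The strongest objection is about scope. A reader might infer that the pandemic assessment of Haem-A-QoL rests on this subset. It does not. It is one of three Covid-19 analyses, the only one that SAP 6.3.2.4 calls supportive, and the other two use recorded deviations rather than how patients feel. It lies outside the testing hierarchy and feeds no decision rule. This objection stands and limits the weight of the point.

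A reader might also infer that the subset necessarily shrinks the arm difference. The documents do not support that. They state no expected effect of fitusiran on anxiety/depression, no correlation and no direction. Protocol 1.1 says only that preventing bleeds may improve quality of life. The size is equally uncertain. A 0.8 SD anxiety shift would move -9 to -6.9 (rho 0.5, 25% worsening), but it exceeds the 9/15 = 0.6 SD effect assumed on Haem-A-QoL itself, so that example should carry no weight. At 0.4 SD the bias is 0.7 to 2.2 points. The standard error of the full-set difference is 15 × √(1/32 + 1/64) = 3.2 points, so bias of this size would be hard to see in one trial.

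Finally, calendar period answers a different question from individual distress, and splitting about 96 evaluable patients costs precision. Both are true. But the deviation-based checks do not capture distress in a patient without a deviation, and this subset cannot attribute distress to Covid-19.

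**Conclusion.** The point holds as a limited one. The third Covid-19 analysis conditions on an open-label response taken after randomization, which treatment may affect and which overlaps with the total score, so its arms are not the randomized arms. It contains no pandemic criterion. Both statements follow from the documents without assumptions.

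Bias is possible. It is most plausibly towards the null if fitusiran improves anxiety: 8% to 24.5% attenuation for a 0.4 SD shift under the inputs above. It is absent if there is no anxiety effect and the correlations are equal in both arms, and the difference is enlarged under other assumptions. The calculation treats a five-level item as a latent normal variable and ignores covariate adjustment, so it illustrates the mechanism and does not forecast a result.

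It would be wrong to conclude that the main Haem-A-QoL result is compromised. The main ANCOVA, the order of testing and the two deviation-based checks are unaffected.

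**What to change.** Replace the subset, as a Covid-19 check, with the same ANCOVA in all patients, adding pandemic period and treatment-by-period. Define period by each patient's scheduled EOS date (Day 1 + 252 days) against a date for each country fixed before database lock. The scheduled date is set at Day 1, so treatment cannot move it. Report the arm difference within each period with its confidence interval.

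Keep the change in EQ-5D anxiety/depression as a descriptive table by arm, beside the level counts already planned in SAP 6.3.3.3. If the subset is retained, label it descriptive, report the share of patients kept in each arm, and draw no Covid-19 conclusion from it.

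The cost is SAP wording, a list of country dates and one model on dates already recorded. The downside is precision. With SD 15 and an even split of 32 and 64 patients, each period's difference has a standard error of 15 × √(1/16 + 1/32) = 4.6 points, and the contrast between periods has 4.6 × √2 = 6.5. It is worse if few assessments fall in one period, or once patients under 17, who do not complete Haem-A-QoL, are left out.

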6.3.2.5 ABR in the onset period

Analysis will include all bleeding episodes between Day 1 visit and Day 28 (inclusive). The primary efficacy analysis will be repeated with this endpoint. No formal hypothesis testing will be performed; p-value will be deemed exploratory.

6.3.3 Exploratory endpoints

6.3.3.1 TSQM-9

The Treatment Satisfaction Questionnaire for Medication (TSQM) version 9 will assess patient satisfaction with treatment. The TSQM Scale scores and their changes from baseline will be summarized.

6.3.3.2 HAL and pedHAL

The Haemophilia Activities List (HAL, in patients ≥ 18 years of age) and pediatric HAL (pedHAL, in patients < 18 years of age) questionnaires assess subjective functional ability to perform activities of daily living. Overall score, component scores, domain scores, and their changes will be summarized by scheduled visits.

6.3.3.3 EQ-5D-5L

The EQ-5D-5L is a standardized instrument for use as a measure of QOL outcome. Index value and visual analogue scale (VAS) score and their changes from baseline will be summarized. Numbers and percentages of patient by level and dichotomized level (1 = no problems, 2 to 5 = “problems”) of each dimension will be reported.

6.3.3.4 Haemo-QOL

The Haemo-QOL will be provided to patients < 17 years of age. The change from baseline in total score of Haemo-QOL will be analyzed using an analysis of covariance (ANCOVA) model with fixed effects of treatment arm, randomization strata of number of bleeding episodes in the 6 months prior to study entry (≤ 10 vs > 10) and randomization strata of hemophilia type (A vs B), baseline Haemo-QOL total score as a covariate. Domain scores for Haemo-QOL and their changes from baseline will be summarized descriptively. Only the descriptive statistics will be provided if ANCOVA model does not converge due to the small sample size.

6.3.3.5 Number of target joint bleeding episodes

A target joint is defined as a joint where 3 more spontaneous bleeding episodes in a single joint within a consecutive 6-month period have occurred. The target joints are identified at baseline and their bleeding episodes are captured and monitored during the study. An exploratory analysis of the number of target joint bleeding episodes may be performed using the same negative binominal model as the primary analysis.

